#### 9.3 Planned Analyses

The analyses described in this section will be performed for data captured in Study Part 1 and Study Part 2 separately. No formal statistical inference is planned for data captured in Study Part 1.

As a general strategy, continuous efficacy and safety endpoints will be summarized using the five-number summary (mean, standard deviation, median, minimum, and maximum). Frequency distributions (counts and percentages) will be used to summarize categorical endpoints.

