2.3 Exploratory Objectives

[figure not shown]
The exploratory objectives of Part 1 of the study:

- Evaluate clinical improvement using National Early Warning Score 2 (NEWS2)
- Evaluate the need and duration of rescue therapy
- Evaluate the effect on subjective symptoms of COVID-19
- Evaluate progression of COVID-19 from moderate or severe to more severe (i.e., moderate to severe, moderate to critical, or severe to critical)
- Evaluate the effect of ANA001 on requirement for oxygen and/or assisted ventilation
- Evaluate time to resolution of the WHO Ordinal Scale for Clinical Improvement
- Evaluate the effect of ANA001 on thromboembolic events
- Evaluate the relationship of ANA001 and markers of inflammation associated with acute respiratory distress syndrome (ARDS)

• Evaluate the relationship between ANA001 plasma concentrations and viral dynamics

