4.2.2 Exploratory Efficacy Endpoints

The following are the exploratory efficacy endpoints of Part 1 of this study:

- Mean change from baseline in the NEWS-2 total score on Day 15
- Mean number of days on rescue treatment (COVID-19 therapies that are FDA approved or have emergency-use authorization) within 15 days after enrollment.
- Median time (in days) to resolution of subjective symptoms assessed by the Investigator to be potentially due to COVID-19 including: fever, cough (productive or non-productive), sore throat, malaise, headache, muscle pain, gastrointestinal symptoms (i.e., nausea, vomiting, or diarrhea), shortness of breath (with or without exertion), and respiratory distress
- Proportion of participants who's COVID-19 progresses to Severe or Critical within 15 days after enrollment
- Proportion of participants requiring ICU admission within 15 days after enrollment
- Mean change from baseline in SOFA score on Days 8 and 15
- Proportion of participants on Days 8 and 15 requiring:
 - Supplemental oxygen
 - High flow nasal cannula (HFNC) oxygen
 - Non-invasive positive pressure ventilation (NIPPV)
 - Mechanical ventilation
- Mean number of days on mechanical ventilation within 15 days after enrollment
- Mean number of oxygenation-free days within 15 days after enrollment

- Proportion of participants who achieve a score of 1 on the WHO Ordinal Scale for Clinical Improvement on Days 8 and 15
- Median time (in hours) to a 2-point improvement in the WHO Ordinal Scale for Clinical Improvement
- Incidence and severity of thromboembolic events within 15 days after enrollment
- Incidence of abnormal markers of inflammation to include CRP, IL-6, TF, MCP-1, and IP-10 on Day 8
- Mean change in viral load from baseline on Days 1, 4, 8, 15, and 28
- Median number of days to viral load undetectable by nasopharyngeal (NP) swab

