7.3 Treatment Exposure and Compliance

Number of doses received, treatment duration (in days) and percent of treatment compliance and compliance category (<80%, 80%-120%, >120%) will be summarized by treatment group for all participants in the Full Analysis Set.

COVID-19 rescue medications will be classified according to the anatomical therapeutic chemical (ATC) codes in the World Health Organization Drug (WHODRUG) dictionary; version B3 WHO Drug DDE – March 2020. The incidence rate of each classified medication will be tabulated by treatment group for all participants in the intent-to-treat population.

Concomitant medications will be classified and tabulated in a manner similar to rescue medications.

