7.5 Efficacy Analysis for Exploratory Endpoints

As a general strategy, analyses of the exploratory efficacy endpoints will be presented for all participants in the Full Analysis Set.

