7.5.2 Number of Days on COVID-19 Rescue Therapy

According to the protocol, participants are allowed to receive concomitant treatments during the course of the study per the standard-of-care at the investigational site. Some concomitant treatments (*e.g.*, treatments granted US FDA approval, Emergency Use Authorization or glucocorticoid therapy) may aid the cure of COVID-19. For the purpose of this analysis, medications that may have direct anti-viral effects or systemic effects on the acute inflammatory processes of the virus/COVID and are given more than 24 hours after study drug started and no more than 240 hours (10 days) after enrollment will be considered COVID-19 rescue therapy. All concomitant medications will be reviewed in a blinded fashion prior to the database lock by team members with appropriate background and training to identify concomitant treatment that may be considered COVID-19 rescue therapy.

Mean number of days on COVID-19 rescue treatment within 15 days after enrollment will be tabulated by treatment group. The difference in the least-squares mean and their standard errors adjusted for stratification factors, baseline WHO Ordinal Scale for Clinical Improvement score, and number of co-existing conditions will be tabulated. Corresponding 95% confidence interval of the difference between two least-squares means and p-value will also be reported.

Participants who do not require any COVID-19 rescue treatment during the study will be excluded from the analysis of this endpoint.

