7.5.5 ICU Admission

The number and proportion of participants requiring ICU admission at any time within the first 15 days after enrollment will be tabulated by treatment group and Baseline WHO Ordinal Scale for Clinical Improvement score. The corresponding 95% binomial confidence interval will also be reported. Sample size permitting, Wilson's method will be used to derive these confidence intervals. The difference in proportions will also be reported with the corresponding 95% confidence interval using Newcombe's method. Should the number of observed admissions be small, the exact distribution will be used instead of the normal approximation to derive the confidence intervals.

Participants who did not get admitted to ICU will not contribute to this analysis

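### Two Part 1 exploratory analyses keep only participants who had the event, so the ICU proportion is about 100% in each arm and mean rescue days ignores avoided rescue and can reverse sign

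*SAP*

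**What the plan says.** SAP 7.5 gives the general strategy for this group of endpoints: "analyses of the exploratory efficacy endpoints will be presented for all participants in the Full Analysis Set". SAP 5.1 defines that set as everyone randomised, in the arm assigned.

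Two subsections then narrow the set.

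- **Rescue days (SAP 7.5.2).** Mean days on rescue within 15 days of enrolment are compared by adjusted least-squares means, with a 95% confidence interval and a p-value. The section ends: "Participants who do not require any COVID-19 rescue treatment during the study will be excluded from the analysis of this endpoint". The objective in SAP 2.3 is wider: "Evaluate the need and duration of rescue therapy".
- **ICU admission (SAP 7.5.5).** The number and proportion admitted within 15 days are tabulated by arm, with Wilson intervals, a Newcombe interval for the difference, and exact intervals if admissions are few. The section ends: "Participants who did not get admitted to ICU will not contribute to this analysis". The endpoint in SAP 4.2.2 has no such restriction: "Proportion of participants requiring ICU admission within 15 days after enrollment".

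The ICU sentence also closes SAP 7.5.6 (SOFA). It fits there, because the protocol's schedule of events collects post-baseline SOFA only in ICU participants.

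**The concern.** Needing rescue and being admitted to ICU both happen after randomisation, and the drug may affect either. An analysis limited to participants with the event no longer compares the randomised groups.

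For ICU admission, numerator and denominator become the same people, so the proportion says nothing about how often ICU was needed. For rescue days, a participant spared rescue disappears from the analysis instead of counting as 0 days. If the drug mainly prevents short courses, its remaining users are those with longer courses, and the drug can look harmful in the only planned comparison of rescue days.

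The stakes are limited but real. Protocol 9.3 says of Part 1: "No formal statistical inference is planned for data captured in Study Part 1". However, Protocol 6.6.2 lets the sponsor change the Part 2 sample size or endpoints in the light of Part 1 efficacy data. Rescue days is also the second secondary endpoint in the Part 2 testing order (Protocol 9.7). This SAP covers Part 1 only, and nothing in the documents shows that the rule would be carried into Part 2.

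**Working it through.** The plan states no figure for either analysis, so there is none to reproduce. Arm size is 30 (Protocol 9.1.1). **All event rates and durations below are assumptions.** Differences are ANA001 minus placebo.

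**ICU admission.** The Newcombe interval is built from Wilson limits (l, u) for each proportion p, with d = p1 - p2:

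lower = d - √[(p1 - l1)² + (u2 - p2)²]; upper = d + √[(u1 - p1)² + (p2 - l2)²]

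Assume 3 admitted on ANA001 and 9 on placebo, all by Day 15.

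- Full Analysis Set: 3/30 = 0.10 (Wilson 0.035 to 0.256) and 9/30 = 0.30 (0.167 to 0.479).
  - d = -0.20
  - lower = -0.20 - √(0.065² + 0.179²) = -0.390
  - upper = -0.20 + √(0.156² + 0.133²) = +0.005
- As written: 3/3 = 1 (0.439 to 1) and 9/9 = 1 (0.701 to 1).
  - d = 0
  - lower = -(1 - 0.439) = -0.561
  - upper = 1 - 0.701 = +0.299

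| Admitted (ANA001, placebo) | Full Analysis Set, points (95% CI) | As written, points (95% CI) |
|---|---|---|
| 3, 9 | -20.0 (-39.0 to +0.5) | 0 (-56.1 to +29.9) |
| 2, 8 | -20.0 (-38.4 to -0.7) | 0 (-65.8 to +32.4) |
| 1, 9 | -26.7 (-44.8 to -7.8) | 0 (-79.3 to +29.9) |

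The as-written difference is 0 whatever the effect, and its interval reflects only how many were admitted. If an arm has no admissions, the proportion is undefined. It falls below 100% only if participants first admitted after Day 15 stay in the denominator. One such ANA001 participant gives 3/4 against 9/9, or -25.0 points (-69.9 to +11.2), so an extra admission makes the drug look better. One in each arm gives 3/4 against 9/10, or -15.0 points. Exact intervals would not change any point estimate.

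**Rescue days.** Counting non-users as 0:

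all-participant mean = P(any rescue) × mean days among users

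Assume 60% of placebo participants use rescue, averaging 5 days: 0.6 × 5 = 3.0.

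| ANA001 use | ANA001 users' mean | All-participant mean | All-participant difference | Users-only difference |
|---|---|---|---|---|
| 40% | 4 d | 1.6 | -1.4 | -1.0 |
| 40% | 5 d | 2.0 | -1.0 | 0 |
| 40% | 6 d | 2.4 | -0.6 | +1.0 |
| 30% | 7 d | 2.1 | -0.9 | +2.0 |
| 50% | 5.5 d | 2.75 | -0.25 | +0.5 |

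The sign reverses when ANA001 users average more than 5 days while the all-participant mean stays below 3.0. At 40% use that means between 5 and 3.0/0.4 = 7.5 days. At 50% use it means between 5 and 3.0/0.5 = 6 days. With 60% and 40% use, the comparison rests on 0.6 × 30 = 18 and 0.4 × 30 = 12 participants.

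**A mechanism for longer courses among users.** Suppose 9 placebo participants have 3-day courses and 9 have 7-day courses. The placebo mean is (27 + 63)/30 = 3.0 over all and 90/18 = 5.0 among users. Suppose the drug prevents the 9 short courses and cuts the long ones to 6 days.

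- All participants: 54/30 = 1.8, difference -1.2 days.
- Users only: 6 - 5 = +1.0 day.
- If long courses fall to 4 days instead, both analyses favour the drug (-1.8 and -1.0).

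**Simulation.** There were 20,000 runs with 30 per arm. On placebo, 40% had no rescue, 30% short courses around 3 days and 30% long courses around 7 days. The drug averted 67% of short courses and shortened long ones by 1 day. The average difference was -0.91 days over all participants and +0.24 among users. The users-only estimate pointed against the drug in 58% of runs.

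**The case against.** **The ICU sentence looks like a slip.** It matches the close of SAP 7.5.6, and intervals for a proportion make little sense once only admitted participants count. SAP 7.5.8, on the WHO scale, still speaks of admissions, so text was evidently copied between sections. A sensible analyst might use the full denominator anyway, and a reader could rebuild 3/30 and 9/30 from the tabulated counts and arm sizes. Misplacement is a fair inference and makes the correction easy, but the sentence is explicit and governs 7.5.5 until removed.

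**SAP 7.5 is worded as a general strategy.** It therefore allows exceptions. That softens the conflict with SAP 7.5, but not the conflict with the endpoint in SAP 4.2.2 or the objective in SAP 2.3.

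**Need for rescue is covered elsewhere.** SAP 7.3 says of rescue medications: "The incidence rate of each classified medication will be tabulated by treatment group for all participants in the intent-to-treat population". That table is useful, but it is arranged by medication class. It compares neither the overall need for rescue nor rescue days between arms.

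**The excluded group may not be exactly those with zero counted days.** The exclusion refers to rescue during the study, and the SAP section 6 definition has no time window, whereas 7.5.2 counts only medication given more than 24 hours after study drug started and "no more than 240 hours (10 days) after enrollment will be considered COVID-19 rescue therapy". Someone treated only outside that window might remain as a zero. This stands as an ambiguity. It could keep in a few zeros by accident, but would not restore participants who never had rescue.

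**The sizes are assumed, and the endpoints are exploratory in 60 participants without multiplicity control.** Both are true. They limit the importance of the point and show that reversal is possible rather than certain.

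**Conclusion.** The concern holds. Under the literal text, the ICU proportion is about 100% in any arm with admissions and its between-arm difference cannot measure an effect. This follows from the definition, apart from first admissions after Day 15. The users-only rescue comparison is not protected by randomisation. It credits shorter courses but not avoided ones, and can be null or favour placebo when total rescue days fall.

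The illustrative sizes are -20 points turned into 0 for ICU admission, and -0.6 days turned into +1.0 for rescue. They depend on assumed rates with 30 per arm, and under other rates the two rescue analyses agree in sign. Because both endpoints are exploratory, this is a should-fix.

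**What to change.** - **ICU (SAP 7.5.5).** Delete the exclusion sentence. Use all Full Analysis Set participants in the arm as the denominator, and count those not admitted by Day 15 as non-events.
- **Rescue days (SAP 7.5.2).** Delete the exclusion sentence. Score participants without rescue as 0 days and analyse the whole Full Analysis Set. Keep mean days among users and the proportion needing rescue as descriptive additions.
- **Deaths and incomplete follow-up within 15 days.** State a rule so that early death or withdrawal does not pass for few rescue days. One option is a rank-based analysis with death ranked worst, with imputed days for withdrawals and a sensitivity analysis.
- **Sections that cite 7.5.5 (7.5.7 to 7.5.10).** Say that they borrow only its interval methods, not its denominator.
- **Windows in 7.5.2.** Say whether the 240-hour limit only defines which medications qualify or also limits the days counted within 15 days.
- **Part 2.** Do not carry the users-only rule into a Part 2 SAP.

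The cost is SAP wording, and no new data are needed. Rescue days will contain many zeros, so a rank-based or bootstrap check should accompany the least-squares means. The rule for deaths and follow-up must be fixed before unblinding.

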7.5.3 Duration of COVID-19 Symptoms

Subjective symptoms assessed by the investigators to be potentially due to COVID-19, including fever, cough (productive or non-productive), sore throat, malaise, headache, muscle pain, gastrointestinal symptoms (i.e., nausea, vomiting, or diarrhea), shortness of breath (with or without exertion), and respiratory distress will be captured and followed up until resolution.

Duration (in days) to resolution of subjective COVID-19 symptoms will be defined as:

End date of last COVID-19 symptom – Start date of first COVID-19 symptom+1.

Participants who did not have resolution of COVID-19 symptoms are censored at date of completion/withdrawal. Kaplan-Meier curves will be constructed to duration of COVID-19 symptoms for participants in each treatment group. The curves will be constructed in a manner similar to the primary efficacy endpoint (Section 7.4). Median duration of COVID-19 symptoms and corresponding 95% confidence interval will be presented for each treatment group.

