### 5.3 Inclusion Criteria

To be included in this study, an individual must satisfy all the following criteria:

- 1. Willing and able to provide written informed consent (or their legally authorized representative) prior to performing study procedures. If necessary, emergency consent may be obtained per local procedures.
- 2. Hospitalized.
- 3. Understands and agrees to comply with planned study procedures, including ability and willingness to swallow multiple small capsules.
- 4. Male or female adult  $\geq$ 18 years of age at the time of informed consent.
- 5. Positive for SARS-CoV-2 by a standard RT-PCR assay or alternative Sponsor approved assay within 7 days of randomization and no more than 36 hours after hospitalization.
- 6. Presence of symptoms of lower respiratory tract infection (LRTI) including at least 1 of the following: fever, cough, sore throat, malaise, headache, muscle pain, or more significant lower respiratory tract symptoms, including shortness of breath (at rest or with exertion).
- 7. At least 1 of the following: respiratory rate (RR) ≥20 breaths per minute, room air SpO2 <98%, requirement for supplemental oxygen, heart rate (HR) ≥90 beats per minute, or temperature >38.3°C.
- 8. Access to a telemedicine platform for outpatient visits in cases where visits to the study site are not possible (e.g., telephone, smartphone, tablet, or computer).
- 9. Women of childbearing potential must agree to abstinence from heterosexual intercourse or use at least 1 form of contraception not including hormonal contraception from the day of screening through Day 30.

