#### **6.1** Screening Period Assessments

The screening procedures and evaluations are to be carried out prior to the start of treatment. Screening assessments are to be performed and completed no more than 36 hours before randomization, and as soon as possible following hospital presentation. Randomization and initiation of treatment should occur as soon as possible following confirmation that all inclusion and no exclusion criteria have been met. Screening and Day 1 may occur on the same day if eligibility criteria are met. Assessments to be performed and information to be collected for the Screening period include:

- Obtain informed consent. No study specific assessments will be conducted until after provision of written informed consent.
- Demographics.
- Eligibility assessment.
- Medical history or current presence of signs and symptoms associated with COVID-19 within 14 days prior to screening, including fever, cough (productive or non-productive), sore throat, malaise, headache, muscle pain, gastrointestinal symptoms (i.e., nausea, vomiting, or diarrhea), shortness of breath (with or without exertion), and respiratory distress. Other medical history within 14 days prior to enrollment and the presence of comorbidities, especially cardiovascular disease, pulmonary disease (e.g., COPD, asthma), hypertension, diabetes, and obesity, is to be recorded as well.
- NEWS2 (Appendix 2), vital signs, severity of the participant's COVID-19 (Appendix 4), and assessment for presence of subjective clinical signs and symptoms of COVID-19 will be assessed and include presence or absence of: fever, cough (productive or non-productive), sore throat, malaise, headache, muscle pain, gastrointestinal symptoms (i.e., nausea, vomiting, or diarrhea), shortness of breath (with or without exertion), and respiratory distress.
- Record SpO2 on room air and need for supplemental nasal cannula oxygen (including flow rate) if applicable. If clinically possible, SpO2 should be recorded on room air for all patients and if applicable a value should be recorded on supplemental oxygen (with at least 30 continuous minutes of oxygen administration).
- Targeted physical examination.
- Nasopharyngeal (NP) swab for confirmation of SARS-CoV-2 with RT-PCR or Sponsor approved alternative test (e.g., local laboratory analysis used for screening).
- WHO Ordinal Scale for Clinical Improvement score (Appendix 1) assessment.
- Chest X-ray per local standard-of-care.

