4.1 Demographic and Baseline Disease Characteristics

Demographics characteristics include:

- Age at baseline (including number of participants 18 40, 40 65, and ≥ 65 years)
- Sex at birth
- Ethnicity
- Race
- Height (m)
- Weight at Baseline (kg)
- Body mass index at Baseline (kg/m2) (including number of participants $> 30 \text{ kg/m}^2$).

Baseline disease characteristics include:

- WHO Ordinal Scale for Clinical Improvement score
- Number of days from first symptom to randomization
- Number of COVID-19 symptoms
- Number of co-existing conditions (0, 1, 2, 3, ≥4) as determined by medical history and other screening data, including
 - Age at screening >60 years
 - $\circ~$ Obesity, which is defined BMI at screening >30 kg/m^2 $\,$
 - Hypertension
 - Cardiovascular disease
 - Chronic lung disease
 - Chronic kidney disease
 - Chronic liver disease
 - Chronic immunosuppression, and
 - o Diabetes
- Respiration rate (<20, ≥ 20 to <25, ≥ 25 to <30, and ≥ 30 breaths per minutes)
- Pulse rate (<90, ≥ 90 to <100, ≥ 100 to <125, and ≥ 125 beats per minute)
- Temperature (\leq 38.3 versus > 38.3C)

- Peripheral capillary oxygen saturation (SpO₂) (>93% and <98% on room air versus <93% on room air)
- Fraction of Inspired Oxygen $(SpO_2/FiO_2) (\leq or > 200)$

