5.2 Subgroups

Sample size permitting, the following subgroups will be considered:

- Age at baseline: $18 40, 40 <65, \ge 65$ years
- Sex: Male, Female
- Ethnicity: Hispanic or Latino, Not Hispanic or Latino
- Race: While, African American/Black, Asian, Other
- Symptoms duration: $< 7 \text{ days}, \ge 7 \text{ days}$
- Baseline score of the WHO Clinical Improvement Scale: 3, 4
- Co-existing conditions: chronic lung disease, cardiovascular or cerebrovascular disease, hypertension, diabetes, obesity, an immunocompromised state
- Peripheral Capillary Oxygen Saturation (SpO₂): > 93% and < 98% on room air versus \leq 93% on room air.

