7.4. Efficacy Analysis for Secondary Endpoint

The secondary efficacy endpoint for Part 1 of this study is the median time (in hours) from randomization to hospital discharge (where discharge is defined as a score of 1 or 2 in the WHO Ordinal Scale for Clinical Improvement).

Kaplan-Meier curves will be constructed to display time-to- hospital discharge. Participants who are lost to follow-up or ended study early prior to achieving clinical improvement will be censored at the day of the last obtained assessment of their WHO Ordinal Scale for Clinical Improvement. Participants who complete follow-up without hospital discharge will be censored at the day of their Day 60 visit. Participants who die for any reason during the study will be right-censored at Day 60 or date of death, whichever is earlier. For the analysis of this efficacy endpoint, missing scores of the WHO Ordinal Scale for Clinical Improvement will be assumed to be > 2 (*i.e.*, no hospital discharge). Median time-to-clinical improvement and corresponding 95% confidence interval will be estimated from the Kaplan-Meier curves and tabulated for each treatment group.

The Cox proportional hazard method will be used to calculate the hospital discharge rate ratio of ANA001 relative to placebo while controlling for the stratification factors, baseline WHO Ordinal Scale for Clinical Improvement, and number of co-existing conditions. Hospital discharge rate ratio is akin to a hazard ratio but for the beneficial outcome of hospital discharge.

A hospital discharge rate ratio > 1 indicates a benefit for ANA001. Treatment groups will be compared using a stratified log-rank test.

The above analyses will be produced for all participants in the Full Analysis Set and by baseline WHO Ordinal Scale for Clinical Improvement scores. Additionally, the same analysis will be produced for participants in the Per-Protocol Analysis Set and Safety Analysis Set.

If WHO Ordinal Scale are missing at baseline, 6 hours window after first dose will be added for baseline values.

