7.5.11 Viral Dynamics

Observed mean and mean change in log-transformed viral load from baseline on Days 1, 4, 8, 15, and 28 will be tabulated by treatment group and compared similar to the analysis of the SOFA score in Section 7.5.6.

Time-to-viral load undetectable (*i.e.*, <LOD) by nasopharyngeal swab is defined as the number of days from randomization to achieving undetectable viral load. That is:

(Date/Time to Undetectable Nasopharyngeal Swap – Date/Time of Randomization)/24.

Participants who are lost to follow-up or ended study early prior to achieve Undetectable Nasopharyngeal Swap will be censored at the day of the last obtained assessment. Median

number of days to undetectable will be tabulated by treatment group and compared in a way similar to the analysis of duration of COVID-19 symptoms in Section 7.5.3.

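### SAP 7.5.3 counts time to symptom resolution from first symptom, not from randomization, so the reported medians are total illness durations and the comparison carries avoidable noise

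*SAP*

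**What the plan says.** SAP 4.2.2 lists the exploratory efficacy endpoint as "Median time (in days) to resolution of subjective symptoms assessed by the Investigator to be potentially due to COVID-19" and states no time origin. SAP 7.5.3 supplies one: "End date of last COVID-19 symptom – Start date of first COVID-19 symptom+1". It specifies Kaplan-Meier curves built like those of Section 7.4, a median with 95% confidence interval per arm, and censoring at completion or withdrawal.

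Two other time-to-event endpoints state a different origin. SAP 7.4 analyses "median time (in hours) from randomization to hospital discharge". In SAP 7.5.11, time to undetectable virus is "defined as the number of days from randomization to achieving undetectable viral load".

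Onset precedes randomization by design. Protocol 5.3, criterion 6, requires "Presence of symptoms of lower respiratory tract infection (LRTI) including at least 1 of the following" (a list of symptoms follows). Protocol 6.1 collects "Medical history or current presence of signs and symptoms associated with COVID-19 within 14 days prior to screening". The SAP treats the interval itself as baseline information: Section 4.1 lists "Number of days from first symptom to randomization" as a baseline disease characteristic, and Section 5.2 plans a "Symptoms duration" subgroup split at 7 days.

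**The concern.** Days between first symptom and randomization cannot contain a resolution event in an eligible participant, and treatment cannot change them. Under 7.5.3 they still count in the outcome, so one interval serves both as a baseline variable and as part of an efficacy endpoint. The section has no delayed-entry handling, no adjustment for the interval and no sensitivity analysis from randomization.

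Two things are at stake. A reader who sees a median time to resolution will take it as time after treatment starts, and it is not. And people with long and short histories are mixed in the same risk sets, which adds variability unrelated to treatment to any comparison of the arms.

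**Working it through.** **The plan's own figure.** The documents give no power or median for this endpoint. The only powered time-to-event figure is in Protocol 9.1.2, for the Part 2 primary endpoint: medians 15 v 11 days, two-sided 0.05, 85% power, 374 recoveries. Schoenfeld's formula gives 4 × (1.960 + 1.036)² / [ln(15/11)]² = 4 × 8.978 / 0.0962 = 373.3, rounded up to 374. It reproduces, but it serves here only as a source for an assumed rate ratio of 15/11.

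**What the definition does to one participant.** Let R be days from first symptom to randomization and T days from randomization to the end of the last symptom. The SAP value is T + R + 1. With R = 7, each value rises by 8 days.

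**What it does to the medians if R is the same for everyone.** At 15 v 11 the ratio is 15/11 = 1.36. Adding 8 gives 23/19 = 1.21. The difference stays at 4 days. The ordering of event times is unchanged, so a log-rank test and a Cox ratio are unchanged too.

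**What variation in R adds.** The variance of the outcome becomes Var(T) + Var(R). If T is exponential, its SD equals median / ln 2.
- Median 7: SD 10.1, variance 102. An onset SD of 4 to 5 days adds 16 to 25, or 16% to 25%.
- Median 15: SD 21.6, variance 468. The same spread adds 3% to 5%.

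This ignores censoring and is only a guide, but it shows why the loss is larger when symptoms resolve quickly.

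**Simulation.** T was exponential, rounded up to whole days and censored at Day 60. The same trials were analysed from randomization (T) and from onset (T + R, without the extra day). Symptom medians and onset distributions are assumptions. At 188 per arm (1,500 runs per scenario; arrows run from randomization origin to onset origin):

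| Assumed medians | Onset interval R (days) | Medians from randomization | Medians from onset | Difference | Ratio | Log-rank power |
|---|---|---|---|---|---|---|
| 15 v 11 | gamma, mean 7, SD 4 | 15.5 v 11.5 | 22.8 v 18.9 | 4.01 → 3.86 | 1.35 → 1.20 | 84.1% → 82.1% |
| 10 v 7.3 | constant 7 | 10.4 v 7.8 | 17.4 v 14.8 | 2.61 → 2.61 | 1.33 → 1.18 | 83.8% → 83.8% |
| 10 v 7.3 | gamma, mean 7, SD 4 | 10.5 v 7.8 | 17.9 v 15.3 | 2.67 → 2.59 | 1.34 → 1.17 | 84.8% → 80.7% |
| 7 v 5.1 | uniform 1–14 | 7.5 v 5.6 | 15.8 v 14.1 | 1.86 → 1.66 | 1.33 → 1.12 | 84.5% → 79.4% |
| 7 v 5.1 | gamma, mean 7, SD 4 | 7.5 v 5.6 | 14.9 v 13.1 | 1.84 → 1.85 | 1.33 → 1.14 | 83.6% → 77.1% |

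In these runs the rate ratio fell at most from about 1.34 to 1.31. A further run of 3,000 trials with onset SD 5 and medians 7 v 5.1 gave 85.0% → 74.1%, the largest loss (about 11 points). Truncating that onset distribution at 15.5 days, roughly the 14-day history window plus the 36-hour screening window, cut the loss from about 10.6 to 5.5 points.

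**Part 1 size, 30 per arm.** Power from randomization is about 21% to 23%. Examples from 3,000 runs each: 21.5% → 20.6% (15 v 11, gamma SD 4) and 21.3% → 18.9% (7 v 5.1, uniform 1–14). A separate run found losses of about 0.3 to 2.4 points at a placebo median of 15 and 1.4 to 4.2 points at 7. Overall this is roughly 1 to 4 points.

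**Chance imbalance in R at 30 per arm.** The SD of the difference in mean R is SD × √(2/30): 0.77 days for SD 3 and 1.29 for SD 5. By the normal approximation, a difference above 1 day in either direction has probability of about 20% to 44%.

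**The case against.** The strongest defence is that 7.5.3 is headed as a duration of symptoms, reports a median duration, and never claims to measure time under treatment. Illness duration is a coherent description. The section names no test or rate ratio: a comparison is implied only by its link to 7.4 and by 7.5.7, 7.5.8 and 7.5.11, which refer back to it. The endpoint is exploratory, this SAP covers only Part 1 with 60 participants, and Protocol 9.3 plans no formal inference there. Most of this stands and limits the size of the point. It does not remove the mismatch: SAP 4.2.2 lists the quantity as an efficacy time to resolution.

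Four stronger readings are tempting, and the documents do not support them.
- **Biased treatment comparison.** Randomization balances the onset interval on average. A chance imbalance with 30 per arm is random error, and it would be visible because the interval is summarized by arm at baseline.
- **Power loss above 10 points.** This needs the Part 2 size, fast resolution and an onset SD of about 5 days. The documents give no SD, and a gamma distribution with mean 7 and SD 5 puts about 9% of onsets beyond the 14-day history window.
- **Dilution of the reported medians' difference.** That difference is nearly unchanged; the ratio is what shrinks.
- **Every other time-to-event endpoint starts at randomization.** Only discharge and viral clearance say so. Time to 2-point improvement (7.5.8) states no origin.

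**Conclusion.** The point holds as a matter of definition and interpretation. An endpoint listed as time to resolution is computed as total illness duration, and nothing in 7.5.3 corrects for the pre-randomization part. That the origin precedes randomization follows from the documents alone. The sizes do not: the lengthening of about 8 days per arm assumes a mean onset interval of 7 days, and the ratio of medians (about 1.35 to about 1.2) also assumes symptom medians of 15 v 11, borrowed from a different endpoint.

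The cost to a test depends on how much onset varies and how fast symptoms resolve: nothing if the interval is constant, about 1 to 4 points from about 22% at the Part 1 size, and 0 to about 11 points at 188 per arm. The planned 7-day subgroup split shows that the SAP expects some variation. No primary, secondary or safety result is affected. The correction is worthwhile because it is cheap and because Protocol Table 3 repeats the endpoint for Part 2.

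**What to change.** In SAP 7.5.3, define the endpoint as days from randomization to the end of the last COVID-19 symptom, and state that origin in 4.2.2. Keep days from first symptom to randomization as a baseline characteristic, as Section 4.1 already does. If total illness duration is of interest, report it as a separately labelled description. Carry the same origin into the Part 2 SAP.

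The cost is a line or two of SAP wording and a change to one derivation, best made before unblinding. The randomization date and symptom end dates are already needed for planned analyses, so no new data are required.
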